Pilot of a Linguistically Adapted CBSM Intervention with Limited Attention to Culture. We conducted a linguistic translation of CBSM for PC survivors treated for localized disease who were Spanish monolingual men. Based on this preliminary work and literature describing shared cultural processes that may interact with chronic disease management, 75,34 we translated the intervention using a professional company and internal verification and conducted some minor adaptations of the C- CBSM intervention to address how factors such as allocentrism and fatalism impact distress, interpersonal relations, self-management and health behaviors. We then conducted 12 focus group sessions following an iterative approach where we first presented the adapted C-CBSM to interventionists (n=4) and health care providers (n=8; Sessions 1-4) and incorporated revisions, then presented the revised CBSM to ten Hispanic PC survivors (Sessions 5-8) and added further revisions based on their feedback. Finally, we presented the further revised CBSM to interventionists, providers and patients combined (Sessions 9-12) and subsequently derived the final version. The vast majority (85-90%) of interventionists, providers and patients rated the final revision of C-CBSM "highly acceptable" and "highly relevant" to the needs of Hispanic PC survivors. Based on this qualitative work, we conducted a pilot study (N=71; surgery n=32; radiation n=39; all localized PC), ⁹⁸ of this version of CBSM developed following standard adaptation procedures (e.g., information gathering, focus groups, expert & patient review). 75,44 Acceptance rate for fully eligible participants was 42% and attendance was 80%. Assignment to C-CBSM, relative to controls (one-day seminar), showed significant improvements in FACT total, physical and emotional well-being, and EPIC sexual functioning, provided

preliminary data on the feasibility and acceptability (80% attendance), as well as some preliminary efficacy on improving symptom burden and HRQoL for Hispanic PC survivors.

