CBSM & Physiological Adaptation. We documented CBSM's effects on diurnal cortisol, circulating inflammatory markers and pro-inflammatory gene expression in circulating leukocytes. 124 In 84 PC survivors about 10.3 months post surgical or radiation treatment undergoing hormonal therapy, pro- inflammatory cytokines were associated greater symptom burden. Better urinary function pre- to post- CBSM was associated with decreases in both IL-1 (r=-.55) and IL-6 (r=-.40). Similarly, decreases in fatigue across the intervention period were associated with decreases in IL-1 \square (r=.41) and IL-6 (r=.35). We also found that decreases in IL-6 were associated with increases in both physical (r=-.38) and social (r=-.37) functioning, and decreases in anxiety (r=.40), while decreases in IL-1 were associated with decreases in both CES-D depression (r=.40) and an ABS negative mood composite (r=.41; all p's <.05). In stage 0-III breast cancer (BC) survivors, CBSM reduced cortisol, changed circulating numbers of specific leukocyte subsets and cytokine production by T lymphocytes. 121,123,124,125 CBSM-treated BC survivors also showed reductions in expression of leukocyte pro-inflammatory gene pathways and enhanced expression of innate antiviral gene pathways. Genome-wide transcriptional profiling and bioinformatics analyses were conducted at baseline and 6- and 12-months post-CBSM in 79 BC survivors randomized to CBSM or health promotion. At baseline, negative affect was associated with a >50% differential expression of 201 leukocyte transcripts. This included upregulated expression of pro-inflammatory and metastasisrelated genes. CBSM altered leukocyte expression of 91 genes by >50% at follow-up. Effects included downregulation of pro-inflammatory (e.g., IL-1A, IL6, TNFA) and metastasis-related (MMP9) genes and upregulation of Type I interferon (IFN) response genes. Promoter-based bioinformatic analyses showed a decreased activity of NF-kappaB/Rel and GATA family transcription factors and increased activity of IFN response factors and the glucocorticoid receptor, suggesting these as mediators of CBSM-induced reversal of upregulated inflammatory gene expression. 124 Although highly efficacious, active treatment (e.g., surgery & radiation; $\sim 70\%$ of cases) for localized prostate cancer (PC) can lead to significant symptom burden (i.e., sexual & urinary dysfunction) and compromises in multiple facets of health related quality of life (HRQoL). Hispanic PC survivors are at a physical and psychosocial disadvantage, yet evidence based treatments (EBTs) such as cognitive behavioral stress management (CBSM) that have proven effective in reducing symptom burden and improving HRQoL in cancer survivors have rarely targeted Hispanics or delivered culturally adapted CBSM in Spanish to diverse Hispanics in the context of a randomized behavioral clinical trial with an adequate sample size and long-term followup. This study will fill several critical gaps in our knowledge on the incremental efficacy of culturally adapted EBTs, relative to standard linguistic translations, on improving symptom burden and HRQoL in Hispanic men with localized PC, and map sociocultural, psychosocial and molecular mechanisms involved in the efficacy of CBSM, and therefore help guide targeted treatments for this critically understudied population and other Spanish speaking cancer survivors.

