To Test Exploratory Hypotheses. Aim 3: For Hypotheses 3, the linear mixed model will include fixed effects for the experimental group (C-CBSM vs. CBSM) and observation time (T1-T4), and random effect for person with a compound symmetry covariance structure for the repeated residuals within person. A group by time interaction and post-hoc tests on this model effect will indicate whether and how the time course of the dependent variable differs between the groups. Hypotheses 1-3 will all be analyzed in a similar manner using the outcome measures described in sections C.6.c (Primary Outcomes), C.6.d (Intervention Targets) and C.6.e (Inflammation) respectively. These measures include markers of symptom burden, systemic inflammation, and cytokine production following cellular activation with TLR ligands. Data from gene expression profiling are analyzed using advanced bioinformatics techniques, and described in C.6.e, and as reported previously by Antoni et al.¹²⁴ As each outcome across the different study hypotheses have been carefully selected to address a priori hypotheses, no adjustment for testing of multiple outcomes will be made. However, within the analysis of a specific outcome, Tukey or Bonferroni adjustment will be made for the multiple tests across different time points. The power calculation below adjusts for this multiplicity. Aims 4a-4c: These hypotheses involve tests of proposed mediators of C-CBSM's effect on our primary outcomes. To test mediation with LGM, individual change trajectory (in each outcome of interest) is characterized by an intercept and a slope factor. The overall pattern of change (e.g., linear, quadratic, etc., as informed by analyses for Aims 1-3) for the whole group can be specified by a particular set of coefficients associated with the slope factor. First, we will specify a growth curve model for all participants with an intercept factor representing our outcome of interest at baseline, and the slope factor reflecting the change trajectory in our outcome measure from T1 to T4. For example, to test that increased stress management skills (e.g., MOCS) in the C-CBSM group accounts for reductions in symptom burden (e.g., EPIC-S), we will first test a LGM model without the stress management skills (the mediator) and then test the model with change in stress management skills from T1 to T4. In the model without the stress management skills, we expect that group assignment is not related to baseline symptom burden, but that group assignment will be related to a greater negative change (reduction) in symptom burden scores. In the next step, we will add stress management skills and expect that after adding this mediator in the model, the path between group assignment and symptom burden slope will become non-significant, while the path between the mediator and symptom burden slope is significant thus suggesting mediation. This approach will be applied to test all mediation models in hypotheses 4a-4c. 191,192 Aim 5a-5b: To evaluate moderators and mechanistic pathways of C-CBSM's effects, we will use LMM and latent variable mediation models. For Hypothesis 5a, we will test moderation by including interaction terms between group assignment (C-CBSM vs. CBSM) and each moderator of interest (e.g., SES, acculturation, Hispanic ancestry, treatment type) within the LMM framework. These models will include fixed effects for group, time (T1-T4), the moderator, and the group × moderator and group × time × moderator interactions. A significant three-way interaction (group × time × moderator) will indicate that change in the outcome (e.g., inflammation, symptom burden, HRQoL) over time differs by both treatment group and the level of the moderator. Post-hoc comparisons will clarify the nature of the moderation effects across timepoints. For Hypothesis 5b, we will test whether improvements in cardiometabolic markers (e.g., lipids, fasting glucose, blood pressure) in the C-CBSM group are mediated by reductions in inflammation using SEM. Parallel process LGMs will estimate trajectories for inflammatory markers and cardiometabolic outcomes across time. The indirect effect from group assignment to cardiometabolic outcome slope via inflammation slope will be tested. This approach allows for simultaneous modeling of changes over time, capturing both within- and between-subject effects. Model fit will be evaluated using standard criteria (CFI > .95, RMSEA ≤ .05, SRMR < .08), and significance of indirect effects will be tested using bias-corrected bootstrapped confidence intervals.

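### Exploratory Aim 4 measures mediator and outcome change over the same T1-T4 window, so it can show association but not mediation; the expected sign for EPIC-S is also unreconciled

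*Combined protocol and SAP*

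**What the plan says.** The rule is in the section To Test Exploratory Hypotheses, under Aims 4a-4c. The outcome is a latent growth curve with "the slope factor reflecting the change trajectory in our outcome measure from T1 to T4". The worked example asks whether a gain in stress management skills (MOCS) "accounts for reductions in symptom burden (e.g., EPIC-S"). The model is fitted first without the mediator; the analysts "then test the model with change in stress management skills from T1 to T4". Mediation is suggested if the mediator path is significant and "the path between group assignment and symptom burden slope will become non-significant". The scope is general: "This approach will be applied to test all mediation models in hypotheses 4a-4c".

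On sign, the same example expects that "group assignment will be related to a greater negative change (reduction) in symptom burden scores".

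The shape of the time course is left open, to be informed by the earlier analyses (Test of Study Hypotheses). The list of aims labels Aim 4 exploratory.

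**The concern.** A mediation claim needs the mediator to change before the outcome. Here both changes are taken over the same 12 months, and no choice of curve shape puts one ahead of the other. If men whose symptoms improve then feel less distressed and rate their coping higher, the data look the same as if better coping had improved the symptoms.

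The protocol itself describes the reverse path. Its opening summary says that the sequelae of treatment can raise glucocorticoid release and inflammatory cytokines, which is the reverse of 4c. Background and Significance says that side effects lead to poor psychosocial functioning and mood disturbance, which is the reverse of 4a. Content overlap adds to the problem in 4a: distress and interpersonal function are mediators, while the emotional and social domains of the FACT are outcomes.

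At stake is the mechanism statement. Skills or gene expression could be credited with an effect that runs the other way. For EPIC-S, a reader who follows the stated sign could take a worsening for the hypothesised benefit, or the reverse.

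**Working it through.** **The plan's own figures.** No power or error figure is given for Aim 4. The figures in Power Analyses, for the primary aim, reproduce with 100 per arm and 80% power:
- 5% two-sided: (1.960 + 0.842) × √(2/100) = 0.396, stated as 0.40.
- 1% two-sided: (2.576 + 0.842) × √(2/100) = 0.483 (0.487 from the t distribution), stated as 0.49.

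**Why the rule can fail.** Suppose that group shifts the outcome change Y by d SD and that Y drives the mediator change M with correlation r, while M has no effect on Y. Regressing Y on group and M gives a group coefficient of d(1 − r²) with residual SD √(1 − r²). The z value for group therefore shrinks from d√(n/2) to about d√(n/2) × √(1 − r²). With n = 70 per arm (half of the 140 projected at T4 in Randomization Protocol) and d = 0.4:
- without M: 0.4 × √35 = 2.37
- with M: 2.26 at r = 0.3, 2.05 at r = 0.5, 1.69 at r = 0.7

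Adding a pure consequence of the outcome is enough to push the group path below 1.96.

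**Simulated size.** 4000 trials per cell, 70 per arm. Entries are the share of trials with a significant group effect in which the plan's rule declares mediation:

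| d | r = 0.3 | r = 0.5 | r = 0.7 |
|---|---|---|---|
| 0.4 | 10% | 26% | 46% |
| 0.5 | 6% | 17% | 36% |
| 0.6 | 4% | 11% | 27% |

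Across re-runs the ranges were 4%-13% at r = 0.3 and 10%-48% at r = 0.5-0.7. With 100 per arm the second range was 4% to about 40%. As a share of all trials the figures are smaller. The chance of a significant group effect is about 66%, 84% and 94% at d = 0.4, 0.5 and 0.6, so at r = 0.5-0.7 the range is from 0.11 × 0.94 = 10% to 0.46 × 0.66 = 30%.

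**With four visits.** A second simulation used least-squares slopes at 0, 3, 6 and 12 months, a group effect of 0.4, and earlier outcome change driving later skills with strength 0.3, 0.5 or 0.8 (2000 trials per cell). With 140 men, the plan's rule declared mediation in 7%, 15% and 30% of all trials. Requiring both the group-to-mediator and mediator-to-outcome paths to be significant is no cure: 11%, 28% and 47%. In a time-ordered model (T2 skills predicting T4 outcome, adjusted for T1 skills and for T1 and T2 outcome) the mediator path was significant in 4%-5% of trials, its nominal rate, and both paths in under 1%.

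**What time ordering costs.** With true mediation complete by T2 (assumed: group to mediator 0.5 SD, mediator to outcome 0.4, persistence 0.8; 70 per arm), the model adjusted for T2 outcome detected it in about 5% of trials, against 81% for the concurrent model. With a small added late effect of 0.1 it detected 33%.

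**How firm T2 is as an end of treatment.** Ten weeks is 70/30.44 = 2.3 months. Assessment and Data collection puts T2 at 3 months plus or minus 2, so between 1 and 5 months. Booster review calls run in T2-T3 and in T3-T4 (Preventing Attrition and Reducing Burden).

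**Direction, section by section.**
- Aims 4a-4c: EPIC-S is the example, and the expected change is negative.
- Pilot of a Linguistically Adapted CBSM Intervention: the adapted arm "showed significant improvements in FACT total, physical and emotional well-being, and EPIC sexual functioning".
- Formal Screening Protocol: the EPIC scales assess sexual and urinary function.
- Experimental Design: symptom burden is itself defined as urinary and sexual function.
- Power Analyses: an effect of 0.40 for EPIC-S, with no direction.

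No section states how EPIC-S is scored or whether it is reversed.

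**The case against.** Much of the case on the other side stands.

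- **Size.** No r or d for this pathway comes from the documents, and a significant mediator path is built in when M is generated from Y. The regressions only approximate the planned latent growth model. Full-information maximum likelihood keeps all randomised men, so 70 per arm is pessimistic. The rates illustrate a structural weakness and do not forecast this trial's error rate.
- **Treatment ends by T2.** A reader might infer this and conclude that mediator change after T2 is irrelevant. The documents do not support it: booster calls continue towards T4, and a T2 visit at 1 month would precede the end of the sessions. The shared-window problem does not need this premise.
- **The EPIC-S sign is wrong.** A reader might infer this too. With no scoring or coding stated, the scores could be reversed before analysis, and the hypotheses define benefit as reduced symptom burden. The texts conflict, but an error is not proven.
- **A lagged model should replace the concurrent one.** Adjusting for T2 outcome removes any benefit already present at T2, and detection can fall to about 5%. Replacement would trade false positives for false negatives.
- **Status.** Aim 4 is exploratory, and the plan says only that the pattern suggests mediation.

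None of this supplies a time order, and the plan has no other analysis that does.

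**Conclusion.** The point holds in a limited form. As specified, Aims 4a-4c can show that mediator and outcome change together and that arms differ, but not which came first. Under assumed reverse causation and no mediation, at 70 per arm, the rule declares mediation in about 4%-13% (r = 0.3) to 10%-48% (r = 0.5-0.7) of trials with a significant group effect, and less often at 100 per arm. The size rests on those assumptions; the inability to order cause and effect does not.

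The EPIC-S direction is an unreconciled inconsistency. It leaves two-sided path tests unchanged and affects only how a result is read. The primary test is unaffected by either issue.

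**What to change.** 1. **Order in time.** Keep the T1-T4 growth model and report it as association. Add a prespecified time-ordered analysis: T1-T2 mediator change predicting later outcome, adjusted for T1 mediator and T1 outcome, run with and without T2 outcome. Base any statement about causal order on that analysis, and state its limits:
   - the version adjusted for T2 outcome has little power if mediation is complete by T2;
   - the version without it does not exclude reverse effects that arise before T2;
   - T2 is only nominally post-treatment, given the booster calls and the visit window;
   - for 4c, some T2 blood samples may be missing, since missed samples may be deferred to the next visit or not taken.

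   Flag the FACT emotional and social domains as overlapping in content with the distress and interpersonal mediators. They need not be dropped.
2. **Direction.** State the direction of benefit and any recoding for EPIC-S, EPIC-UIN, FACT-P and the PROMIS scales, and align the expected sign in the Aim 4 example with it.

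The cost is SAP wording and one further exploratory analysis. T2 assessments are already scheduled, so no new data collection is needed. The time-ordered estimate will be less precise, and in some scenarios much less able to detect a true mediator. That is why it is added beside the growth model and does not replace it.

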Study staff will collect medical treatment and disease characteristics (e.g. type of treatment, disease status markers such as Gleason score, PSA, TNM staging, time of diagnosis, etc.) via EMR review after written consent has been obtained by the participant. Free testosterone will be measured via ELISA. Study staff will enter a participant's medical chart after the T1-baseline assessment and screen for the aforementioned characteristics. Study staff will collect this information from participant's medical charts after each in-person assessment. Study staff will also collect these variables relevant to the time when participants were diagnosed with prostate cancer. All medical chart data collected will be used for study data analysis as outlined in the Informed Consent Form (ICF). Any medical conditions other than PC will be evaluated individually to form a comorbidity index using the Charlson comorbidity scale. ¹⁵²

Sociodemographic Characteristics.

We will also collect age, education, employment, relationship status, nativity or years in the US, race, and years of education in the US. Participants will also complete the Abbreviated Multidimensional Acculturation Scale (AMS). 153 Items are rated on a Likert-type scale ranging from 1 to 4 and assess multiple cultural domains. The AMSA has been widely used in research with diverse Hispanics.

Health Information and Biospecimens Collected:

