Hypothesis 2 (Aim 2): C-CBSM will show significantly greater improvements in intervention targets (i.e., improved stress management, and reduced psychological distress and interpersonal disruption) from baseline (T1) to 3-, 6- and 12-month follow-ups (T2-T4) relative to CBSM.

Test of Study Hypotheses. All analyses will be intent-to-treat analyses ¹⁹⁸ and linear mixed models will be used to test Hypotheses 1-2. These models classify time of measurement as a categorical variable in order to give full flexibility to different mean time courses in the two randomized groups. Latent growth modeling (LGM)¹⁸⁵ with relevant covariates is used to test the three sub-hypotheses of Aim 4. Advances in LGM and structural equations modeling (SEM)¹⁸⁶ allow us to blend these methods to test complex models of change¹⁸⁷ as latent growth models. LGM allows for missing data, as well as irregularly spaced measurements across time, time-varying and invariant covariates, accommodation of individual-specific deviations from the mean time trend and estimation of population variance associated with individual effects. Analyses of the first 3 hypotheses inform the functional form of the LGM time course. Software to implement these analyses is available (e.g. Mplus). ^{188,189} The software permits the blending of continuous and categorical data, the specification of linear and nonlinear models of change, and the specification of longitudinal structural models. Adequate model fit will be established by several fit indicators (Comparative Fit Index [CFI] > .95, Root-Mean-Square Error of Approximation [RMSEA] ≤ .05, Standardized Root-Mean-Square Residual [SRMR] < .08). ¹⁹⁰

Exploratory Hypotheses:

Hypothesis 3 (Aim 3): C-CBSM will show significantly greater activation of leukocyte glucocorticoid receptor (i.e., greater sensitivity) and lower inflammatory gene expression (i.e., less activation) pathways from baseline (T1) to 3-, 6- and 12-month follow-ups (T2-T4) relative to CBSM.

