0.81 and 0.42 respectively. With greater effect sizes anticipated in the proposed study, the sample size of at least 100 per arm has sufficient power to detect differences even after adjusting for the analysis of change from baseline to post-intervention time points. Power for C-CBSM's effect on down regulation of inflammatory genes are based on Antoni et al.¹²⁴ study which indicated that the observed effect size was one standard deviation in a sample size of 45 in the experimental condition. Glucocorticoid receptor sensitivity demonstrated similar effects. With a T4 sample size of 100 in the C-CBSM group, effect sizes of 0.48 standard deviations are detectable with 80% power at a 2-tailed Type I error rate of 1%, so that expected effects will be detectable with sufficient power. While pilot data are not available for all outcome measures, the constant in the power calculation regardless of the outcome is the effect size expressed in terms of standard deviations, which is 0.40 or 0.49 depending on whether the Type I error rate is 5% or 1%.

Covariates, Cohort Effects, Intent to Treat & Missing Data. A number of variables (e.g., SES, disease factors) will be considered as possible covariates. These putative confounds will be entered as covariates if correlated with our outcomes (at p<.10). Random assignment should render groups equivalent on covariates and this will be verified post-hoc. We will test differences among cohorts who have completed our conditions by doing an ANOVA within each condition with k levels of cohort. If we find a cohort with differential outcomes (significant Condition x Cohort x Time interaction), we will conduct a Group x Time interaction tested within each cohort, and a Cohort x Time interaction tested within assignment. We have never observed a significant cohort effect in prior CBSM work. We will also use an intent-to-treat approach in that all participants will be retained in the analysis, including those with missing data at time points by using full information maximum likelihood (FIML) estimation. FIML, a recommended state-of-the-art method, 197,198 uses all available data for each participant and provides unbiased estimates of parameters when the data are missing at random.

Cost to the Participants:

There will be no cost to the participants for taking part in this study. All expenses related to the study activities, including laboratory tests done and lab materials.

Risk and Benefits:

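### Exploratory Aims 4–5: the 5a moderator model leaves out two lower-order interactions, and the 4a–4c mediation rule never tests the indirect effect

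*Combined protocol and SAP*

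**What the plan says.** Everything here is in the Data Analysis Plan, mostly under To Test Exploratory Hypotheses.

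**Aim 5a.** The mixed model is to contain "fixed effects for group, time (T1-T4), the moderator, and the group × moderator and group × time × moderator interactions". The decision rule follows: "A significant three-way interaction (group × time × moderator) will indicate that change in the outcome" depends on both arm and moderator level. The moderators are SES, acculturation, Hispanic ancestry and treatment type. Time is categorical (Test of Study Hypotheses: "These models classify time of measurement as a categorical variable"). The Hypothesis 3 model earlier in the same section also lists only group and time as fixed effects, but then relies on "A group by time interaction and post-hoc tests on this model effect". For therapy cohorts, the section on covariates and cohort effects names the corresponding two-way term, "a Cohort x Time interaction tested within assignment". No coding or centring is given. For acculturation, Sociodemographic Characteristics says only "Items are rated on a Likert-type scale ranging from 1 to 4".

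**Aims 4a–4c.** A growth model is fitted first without the mediator. The stated expectation is no group difference at baseline, "but that group assignment will be related to a greater negative change (reduction) in symptom burden scores". The mediator is then added, and mediation is inferred if "the path between group assignment and symptom burden slope will become non-significant, while the path between the mediator and symptom burden slope is significant". The same approach is to serve every 4a–4c model.

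**Aim 5b.** Here the plan does test the indirect effect, with bias-corrected bootstrap intervals.

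**The concern.** A three-way interaction measures moderation of change only when the two-way terms beneath it are in the model. Without group × time, a treatment effect that is the same at every moderator level can load on the three-way term. Without time × moderator, so can a recovery course that differs by, say, treatment type in both arms alike. The first condition is the trial's own Hypothesis 1, so a successful trial would make spurious moderators more likely.

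The mediation rule treats a non-significant direct path as evidence that the path is zero. It cannot recognise partial mediation, and it gets worse at this as the sample grows. The plan expects benefit through both psychosocial and physiological routes, so each mediator taken alone may well be partial.

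At stake are the exploratory statements on for whom and how C-CBSM works.

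**Working it through.** **Plan's own figures.** Power Analyses gives 100 per arm, 80% power and two-sided tests, with detectable effects of 0.40 SD of change at 5% and 0.49 at 1%. From n = 2(z₁₋α/₂ + z₀.₈)²/d²: 2 × 7.849/0.16 = 98.1, so 99 per arm; and 2 × 11.679/0.2401 = 97.3, so 98. Both reproduce. No power is given for Aims 4–5. Below, N=200 is the planned total and N=140 the T4 retention projected under Randomization Protocol. Effect sizes for Aims 4–5 are assumptions. Paired percentages are N=140/N=200.

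**5a: what the three-way term tests.** Take a 50/50 binary moderator and 0/1 product terms. Group, moderator and group × moderator give each of the four cells (N/4 men) its own level. Time gives a common profile. The three-way term gives a separate profile only to the cell with C-CBSM and moderator = 1, so the test compares change in that cell with pooled change in the other three. With no moderation:

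- Group × time δ only: the contrast is δ − δ/3 = 2δ/3, or 0.267 at δ = 0.4. Time × moderator only gives the same.
- Both at 0.4: 0.8 − 0.8/3 = 0.533.

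Under compound symmetry, the mean of three follow-ups minus baseline has variance (1 + 1/3)/2 = 2/3 of the squared SD of change. The contrast variance is (2/3)(4/N + 4/(3N)) = 32/(9N), that is 0.0254/0.0178.

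If group × time is carried over, the term compares the two moderator levels within C-CBSM only. The contrast is then the full time × moderator effect, with variance (2/3)(8/N) = 0.0381/0.0267.

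If software expands the term as class variables (9 df), it tests equal profiles in all four cells. For a single 0.4 effect the noncentrality is N × 0.2²/(2/3).

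| No true moderation, omitted effect 0.4 SD | Noncentrality | Rejection by formula | Simulated |
|---|---|---|---|
| Group × time only, 3 df | 2.8/4.0 | 26/36% | 26/36% |
| Time × moderator only, 3 df | 2.8/4.0 | 26/36% | 29/35% |
| Both, 3 df | 11.2/16.0 | 81/93% | 82/94% |
| Time × moderator, group × time carried over | 4.2/6.0 | 38/52% | 39/50% |
| Class coding, group × time, 9 df | 8.4/12.0 | 48/66% | 46/67% |
| Full model | – | 5% | 4–6% |

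The simulations used 1,500–2,000 trials per cell, four complete visits and correlation 0.6. A second set, with ICC 0.5 and estimated variances, gave 38%, 34% and 94% at 100 per arm for the first three rows, and 4.3–6.6% for the full model.

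Other simulated cases:

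- 0/1 coding with smaller effects: group × time 0.2 SD, 8/12%; time × moderator 0.1 SD, 7/6%, and 0.2 SD, 9/11%.
- ±0.5 coding: about 5% if balanced; 14/20% with a 70/30 moderator and group × time 0.4.
- Four-level ancestry, equal shares, group × time 0.4: 31/38%.
- Centred continuous moderator: group × time only, 5/6%; time × moderator 0.2 SD per SD, 38/50%.
- Acculturation left on its 1–4 scale (mean 2.5, SD 0.6 assumed), group × time 0.4: 61/80%, falling to 6/4% if group × time is carried over.

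**4a–4c: person-level approximation.** M = aG + e and Y = c′G + bM + e, with unit error SDs.

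*Full mediation, a = b = 0.5, c′ = 0.* The total effect is 0.25/√1.25 = 0.22 SD, so z = 0.2236 × √(N/4) = 1.32/1.58, and the total effect is significant in 26/35% of trials. If it is required, that is the rule's ceiling. Simulated: 24/32%, against 84/94% for a Monte Carlo interval for ab. At a total effect of 0.41 SD the figures are 65/79% against 97/100%.

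*Partial mediation, a = b = 0.5, c′ = 0.4.* SE(c′) = 1/√[(N/4)(1 − 0.0588)] = 0.174/0.146, so z = 2.30/2.74 and the direct path is non-significant in only 37/22%. That ceiling falls as N rises. Simulated: 31/20% against 85/94%. With c′ = 0.2: 45/53% against 84/94%.

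*No mediation, a = c′ = 0, b = 0.5.* The direct path is non-significant in 95% of trials and the mediator path is almost always significant, so the two second-step conditions alone claim mediation about 95% of the time. Requiring the total effect brings false claims to 1–3%. Requiring the group-to-mediator path instead brings them to 1–5%.

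*Fitted parallel-process growth model, total effect required (300 trials per cell).* Full mediation at a = b = 0.5: 17/24% against 56/79% for the interval. Full at a = 0.8, b = 0.6: 50/70% against 96/100%. Partial, direct 0.4: 39/38% against 56/79%. Simulation error is up to about 3 points.

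**The case against.** **Shorthand.** The Hypothesis 3 list also omits group × time, yet the next sentence tests it, so 5a may be meant to inherit it. This is a fair reading. It removes the inflation from group × time (5/5% for a binary moderator), but time × moderator is still unlisted, and at 0.4 SD the error is 39/50%. The Cohort × Time mention is weak evidence either way, because there it is a follow-up test.

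**Coding.** The size runs from nominal to 94% depending on choices the plan does not make. With effects of 0.1–0.2 SD and 0/1 binary coding it is 6–12%. That stands, and it is why the claim is that the model can mislead.

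**Post-hoc comparisons.** The plan says these will clarify any moderation. Under class coding with a binary moderator, the listed model uses 7 + 9 = 16 parameters for 16 cells, so its cell means equal the full factorial's and correct contrasts are available. Only the omnibus label is wrong. This does not rescue 0/1 product terms.

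**Mediation reading.** A path can become non-significant only if it was significant before, so a significant total effect is probably intended, and false claims are then rare. This largely stands: the main harm is missed mediation. The total effect is nevertheless worded as an expectation. On the most favourable reading (no total effect required, group-to-mediator path required), full mediation is found in 78–95% of trials, but partial mediation in only 66/68% (direct 0.2) and 33/21% (direct 0.4).

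**Benchmark.** The comparison figures use a Monte Carlo interval, while the method recommended is 5b's bootstrap. In a separate run on change scores at 100 per arm, the bias-corrected bootstrap found 94–96% of true mediation, and indirect-effect tests gave 4–8% false positives when a = 0. The gap remains, with slightly liberal error possible.

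**Conclusion.** The concern holds for exploratory Aims 4 and 5a only; 5b and the inference for Aims 1–2 are unaffected. As listed, the 5a model can report moderators that do not exist. At 0.4 SD with 0/1 coding, the false-positive rate is roughly a quarter to a third for one omitted effect and 82–94% for both. There is no inflation if neither omitted effect exists, if a continuous moderator is centred and only group × time exists, or with ±0.5 codes and a balanced binary moderator. The 4a–4c rule chiefly misses mediation, especially partial mediation. It produces false mediators if neither the total effect nor the group-to-mediator path is treated as a condition.

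The omissions are certain from the text. The sizes rest on assumed effects, compound symmetry and complete data, and the leading mediation figures on a person-level simplification. The change should be made.

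**What to change.** **5a:** list every lower-order term, adding group × time and time × moderator. Test the three-way term on 3 × (levels − 1) df, or 3 df for a continuous moderator. The additions cost 3 + 3 × (levels − 1) degrees of freedom: 6 for a binary moderator.

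**4a–4c:** replace the rule based on loss of significance with the estimated indirect effect and the bootstrap interval already specified for 5b. Report the group-to-mediator path beside it, whether or not the total effect is significant.

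This is two sentences of SAP wording, with the same data and software.
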